6. OBJECTIVES AND OUTCOME MEASURES

Objectives	Outcome Measures	Time point(s) of evaluation of this outcome measure (if applicable)
Primary Objective To compare the rate of any breastfeeding at 3 months of age in infants with breastfeeding difficulties and diagnosed tonguetie who undergo frenotomy and receive breastfeeding support versus those who receive breastfeeding support only.	Any breastmilk feeding at 3 months according to maternal self-report: defined as any breastmilk feeding in the 24 hours prior to the infant reaching three months of age (Dennis, Jackson et al. 2014, McFadden, Gavine et al. 2017). A positive response is indicative of continuation of breastfeeding.	3 months of age
Secondary Objectives To investigate the effect of frenotomy on various important other secondary outcomes measured at first follow-up visit and/or three months of age. To investigate the impact of tonguetie severity and mothers' prior beliefs on the primary outcome.	Mother's breastfeeding self-efficacy: measured using the Breastfeeding Self- Efficacy Scale – Short Form Mother's pain while feeding during the previous 24 hours*: measured using visual analogue scale of the Short Form McGill Pain Questionnaire (SF-MPQ), modified into a Likert-type scale	First follow-up visit (outcomes indicated by *) 3 months of age (all secondary outcomes)
	Amount of breastfeeding support used: measured by total number of contacts (whether face to face or by telephone) with any breastfeeding supporter since the FROSTTIE procedure Infant weight gain: measured as difference in weight for age z-scores between birth and three months of age Infant post-randomisation weight gain: measured as difference in weight for age z-scores between baseline and three months of age	

Exclusive breastmilk feeding*: exclusive breastmilk feeding in the previous 24 hours

Exclusive direct breastfeeding*: exclusive breastfeeding directly from the breast with no bottle feeds of expressed milk in the previous 24 hours

Age of child when s/he last received breastmilk: age when child last received breastmilk, to determine when and whether switch to exclusive formula feeding has occurred

Time spent breastfeeding in previous 24 hours: time in minutes/hours spent breastfeeding in previous 24 hours

Frenotomy in comparator group*: measured by a specific question

Repeat frenotomy*: measured by a specific question

Bleeding following frenotomy or frenulum tear*: measured by a specific question

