Post-procedure adverse events (tongue cut*, scarring, salivary duct damage*): measured by specific questions

Maternal anxiety and depression dimension of EQ-5D-5L*

Maternal health-related quality of life: as elicited by the EQ-5D-5L*

To examine, through an alongside economic evaluation, whether any additional benefits associated with frenotomy are justified by any additional health care resources needed to deliver the intervention

Maternal and infant NHS healthcare resource use: collected at 3 months of age on general practice visits and hospital admissions

To investigate the effect of	Any breastmilk feeding at 6 months	At 6 months of age
frenotomy on breastfeeding rates	according to maternal self-report: defined	
measured at six months.	as any breastmilk feeding in the 24 hours	
	prior to the infant reaching six months of	
	age	

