- Maternal and infant NHS healthcare resource use: collected on general practice visits and hospital admissions

9.6.4. 6 month follow-up

The following data will be collected using maternal self-report (via web-link to data capture platform, telephone, email or post) when the infant is 6 months of age:

 Any breastmilk feeding at 6 months according to maternal self-report: defined as any breastmilk feeding in the 24 hours prior to the infant reaching six months of age

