12.6. Economic evaluation

The economic evaluation will take the form of a cost-consequence analysis and will present outcomes and healthcare costs in a disaggregated manner for both mothers and their infants (Mauskopf, Paul et al. 1998). The perspective of the analysis will be of the NHS and the time-horizon will be a one-year time frame for infants and lifetime for mothers. However, we will also present a cost-utility analysis from the mother's perspective with a time-horizon up to 3 months.

Health outcomes at 3 months of age will include the primary outcome, the maternal anxiety and depression dimension of the EQ-5D-5L, overall health-related quality of life (EQ-5D-5L), and maternal and infant healthcare costs. Healthcare resource use categories using the online data capture platform will collect information on general practice visits and hospital admissions up to 3 months of age. These healthcare resource use categories will be weighted by appropriate unit costs obtained from national sources to estimate the costs in each trial arm (Curtis and Burns 2015, Department of Health 2015). For the within-trial analysis, maternal quality adjusted life days (QALDs) will be derived as the area under the

curve for the health profile created connecting health-related quality of life measures at one week post-intervention and then at 3 months follow-up. To estimate costs (or savings) in each arm of the trial beyond the trial end date, we will employ a validated published economic model (Pokhrel, Quigley et al. 2015). The model evaluates the potential cost savings attributable to increases in breastfeeding rates through different healthcare policies. We will use the observed treatment effect in the trial (breastfeeding rate difference at 3 months of age) and map such value into one of the policies explored in the economic model to extrapolate costs. For infants, we will extrapolate up to one-year follow-up healthcare costs (or savings) associated with gastrointestinal illness, lower respiratory tract infection and acute otitis media. For mothers, we will use the treatment effect to estimate the potential lifetime maternal healthcare costs (or savings) due to breast cancer. These categories of healthcare costs (at one year for infants and lifetime for mothers) will also be included in the cost-consequence analysis.

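### The maternal QALD curve starts one week after the procedure and resource use has no stated start, so costs and QALDs in the within-trial cost-utility analysis cover different periods

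*Protocol*

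**What the plan says.** Resource use appears in three places in the protocol, each with an end and none with a start:

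- Section 6: "Maternal and infant NHS healthcare resource use: collected at 3 months of age on general practice visits and hospital admissions".
- Section 9.6.3 (3-month follow-up): "Maternal and infant NHS healthcare resource use: collected on general practice visits and hospital admissions".
- Section 12.6: the online platform "will collect information on general practice visits and hospital admissions up to 3 months of age".

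Section 12.6 then has these items "weighted by appropriate unit costs obtained from national sources to estimate the costs in each trial arm".

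For effects, section 12.6 obtains maternal QALDs by integrating a utility profile, described so: "curve for the health profile created connecting health-related quality of life measures at one week post-intervention and then at 3 months follow-up". Section 9.5 lists the EQ-5D-5L among the baseline assessments, but the curve does not use it. The cost-utility analysis is given a horizon up to 3 months, again with no start.

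The other cumulative count in the protocol does have a start. Section 6 counts support contacts "with any breastfeeding supporter since the FROSTTIE procedure", although section 9.6.3 counts the same contacts from the first referral.

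**The concern.** A cost-utility comparison needs costs and effects measured over one period. Here the QALD period is fixed to begin about a week after the procedure, while the cost period has no stated beginning. Neither natural start for costs, the procedure or birth, matches the QALD start.

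Two things are at stake, and they differ in kind.

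- **The first week after the procedure.** This week follows randomisation. Health-care use in it would be costed, while any difference in maternal quality of life over the same days is left out of the QALDs. Because allocation can affect this week, its omission can move the estimated QALD difference.
- **The period before randomisation.** Infants enter at any age below 10 weeks, so a question read as running from birth would take in use that allocation cannot affect. Resource use is asked about once, and the baseline list in section 9.5 has no item on earlier GP visits or admissions. If totals were collected from birth, no later analysis plan could separate use before randomisation from use after it.

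**Working it through.** The protocol gives no figure for the length of either window, so there is none to reproduce. The check is calendar arithmetic.

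**Inputs**

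- End of both windows: 3 months of age (sections 6, 9.6.3, 12.6), taken as 365.25/4 = 91.3 days.
- Age at entry, *a* weeks: 2 (the stratification cut, section 9.4), 4 (the pilot threshold, section 7.1) and 10 (the eligibility limit, section 8.2).
- Randomisation on the procedure day: Appendix A places both at the intervention visit.
- QALD start: 7 days after the procedure, since section 9.6.2 puts the visit at approximately one week.

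**Formulas**

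- Costs from birth: B = 91.3
- Costs from the procedure: P = 91.3 − 7a
- QALD window: Q = P − 7

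| Entry age | B (days) | P (days) | Q (days) | P/Q | Share of P outside the QALDs, 7/P | B/Q | Share of B before randomisation, 7a/B |
|---|---|---|---|---|---|---|---|
| 2 weeks | 91.3 | 77.3 | 70.3 | 1.10 | 9% | 1.30 | 15% |
| 4 weeks | 91.3 | 63.3 | 56.3 | 1.12 | 11% | 1.62 | 31% |
| 10 weeks | 91.3 | 21.3 | 14.3 | 1.49 | 33% | 6.38 | 77% |

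The windows match only if costs start at the one-week visit, which no section says.

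**Sensitivity to the visit date.** Appendix A shows the follow-up visit at 7–14. With a 14-day gap, P/(P − 14) is 77.3/63.3 = 1.22 at 2 weeks, 63.3/49.3 = 1.28 at 4 weeks and 21.3/7.3 = about 2.9 at 10 weeks.

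**What the omitted week holds.** Suppose the arms are level at baseline, utility is joined by straight lines, and *d* is the between-arm utility difference at the one-week visit. The omitted area is then 7 × d/2 = 3.5d QALDs. The protocol gives no value for *d*.

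**Noise under a birth start.** At a constant Poisson contact rate over 13 weeks, counting from birth rather than from randomisation multiplies the variance of the count by 1/(1 − a/13). That is 13/11 = 1.18 at 2 weeks, 13/9 = 1.44 at 4 weeks and 13/3 = 4.33 at 10 weeks. These ratios are for counts at one fixed entry age. They are not ratios for costs or for the trial-level cost difference. Section 7.1 expects fewer than 40% of infants to enter at 4 weeks or over, so the larger ratios would apply to a minority.

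**The case against.** A reader might infer that GP visits before randomisation, and the birth admission itself, are counted in the trial-arm costs. The documents do not support that. They say when counting stops and are silent on when it starts. Other wording leans the opposite way: section 7 describes the 3-month contact as post-intervention follow-up, and section 12.6 speaks of a within-trial analysis. The figures of 15% to 77% and the variance ratios therefore hold only on a birth start that no section adopts, and the ratios also need a constant contact rate that nothing in the protocol supports.

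Nor would such counting bias the comparison. Allocation is 1:1 at random, so earlier use is balanced in expectation and largely cancels in the difference between arms.

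The recall period of a questionnaire item also commonly sits in the questionnaire or an analysis plan, neither of which is shown. On its own, a missing start date would be detail properly left to those documents. The contrast with support contacts adds little, because the protocol gives that count two different starts. Finally, the cost-utility analysis is additional to the main cost-consequence analysis, which presents outcomes and costs separately and needs no common window.

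All of this stands. It does not reach the QALD rule, which section 12.6 states outright. That curve begins at one week although an earlier EQ-5D-5L value is collected, and a recall period set elsewhere would align costs with it only by starting at the one-week visit.

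**Conclusion.** The point holds for the mismatch between the cost and QALD periods. Under either natural start for costs, the cost window is longer than the QALD window. From the procedure the excess is about 7 days, or 1.10, 1.12 and 1.49 times the QALD window for entry at 2, 4 and 10 weeks. This assumes a follow-up visit 7 days after the procedure and randomisation on the procedure day. The 10-week figure is at the eligibility limit, not a typical infant.

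Inclusion of use before randomisation is a possibility that the wording leaves open, not something the protocol states. If it happened, it would inflate the arm-level costs and add variance without biasing the cost difference. It still deserves closing off now, because the question is asked only once and totals collected from birth could not be split afterwards.

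The effect is confined mainly to the within-trial maternal cost-utility analysis. The primary outcome is untouched.

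**What to change.** - **Section 12.6, QALDs:** start the area under the curve at randomisation and use three EQ-5D-5L points: baseline, one week post-intervention and 3 months. Appendix A allows baseline data to be taken at a separate visit up to 7 days before the intervention, so say that the baseline value is taken as the value at randomisation.
- **Sections 6, 9.6.3 and 12.6, resource use:** count maternal and infant GP visits and hospital admissions from the same date, randomisation (the FROSTTIE procedure day), in both arms, up to 3 months of age. Put that start into the recall wording of the 3-month question.
- **Section 12.6, alignment:** add a sentence saying that costs and QALDs in the cost-utility analysis share this start date.

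The cost is one recall phrase and slightly more analysis work. The baseline EQ-5D-5L is already collected, so no extra contact or measurement is needed. If the questionnaire already carries this start, only the protocol wording and the QALD rule need to change.

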9.7. Discontinuation/withdrawal of participants from study

Parents will have the right to withdraw their infant from the study at any time.

Parents will be asked for permission for the study team to complete data collection and follow-up, though they may wish to withdraw consent for any aspect of the study including the use of data already obtained. The reason for withdrawal, where provided, will be recorded in the eCRF. If parents who decide to withdraw their child at any stage consent for their child's data to be used, the data will be included within the final analysis. Withdrawn participants will not be replaced as the sample size has been inflated to account for withdrawal/loss to follow-up.

9.8. Definition of End of Study

The end of the trial will be defined as the date when the trial database is locked. An end of trial declaration will be made to the approving REC.

10. INTERVENTIONS

Infants will be randomised to either:

- frenotomy with standard breastfeeding support (intervention arm), or
- no frenotomy with standard breastfeeding support (comparator arm).

Breastfeeding support will include as a minimum: an initial face-to-face assessment of breastfeeding, for example using the LATCH tool (Jensen, Wallace et al. 1994) or BFI assessment tool, and advice on positioning and attachment and at least one follow-up visit, together with drop-in clinic advice as required, but available on more than one day a week. Staff will be asked to check whether infants have received standard vitamin K prophylaxis, or whether there is any family history of haemophilia prior to the procedure.

10.1. Intervention arm

Infants who are eligible for the trial and whose parents consent for them to participate and who are randomised to frenotomy with breastfeeding support will undergo the procedure according to usual hospital practice. Frenotomy will be carried out by the usual trained practitioner for participating hospitals using their normal technique. Frenotomy is usually a quick procedure in which the tongue is lifted and the frenulum (the tissue between the underside of the tongue and the base of the mouth) is divided. Breastfeeding may be conducted immediately post-procedure, and the baby will undergo an immediate post-frenotomy observed feed. Parents will receive further advice on positioning and attachment together with standard post-frenotomy advice concerning bleeding and other post-frenotomy adverse events. Parents will be provided with details about how to access rapid breastfeeding support in the event of ongoing feeding difficulties and an appointment for at least one follow-up visit.

10.2. Comparator arm

Infants who are eligible for the trial and whose parents consent for them to participate and who are randomised to breastfeeding support only will not undergo frenotomy, but at the frenotomy clinic will undergo an immediate observed feed and will receive further advice on positioning and attachment together with standard post-frenotomy advice concerning bleeding and other post-frenotomy adverse events. Parents will be provided with details about how to access rapid breastfeeding support in the event of ongoing feeding difficulties and an appointment for at least one follow-up visit.

11. SAFETY REPORTING

An independent Data Monitoring Committee (DMC) will be established to review the study data and outcomes including safety reports of Serious Adverse Events (SAEs). The DMC will ensure the safety and wellbeing of the trial participants and, if appropriate, make recommendations to the TSC regarding continuance of the study or modification of the protocol. The TSC will have ultimate responsibility for deciding whether the trial should be stopped on safety grounds.

11.1. Adverse events

An adverse event (AE) is any untoward medical occurrence observed in a participant, which may or may not have a causal relationship with the trial intervention. Bleeding following frenotomy (unless excessive) or frenulum tear and post-procedure adverse events (tongue cut, scarring, salivary duct damage) are expected in this population and will be collected as part of standard follow-up and do not require reporting as AEs.

11.2. Serious adverse events

A serious adverse event (SAE) is any untoward medical occurrence that:

- results in death
- is life-threatening
- requires inpatient hospitalisation or prolongation of existing hospitalisation
- · results in persistent or significant disability/incapacity
- consists of a congenital anomaly or birth defect.

Other 'important medical events' may also be considered serious if they jeopardise the participant or require an intervention to prevent one of the above consequences.

The term "life-threatening" in the definition of "serious" refers to an event in which the participant was at risk of death at the time of the event; it does not refer to an event which hypothetically might have caused death if it were more severe.

NOTE: Congenital anomalies may be identified in the participants of this trial during their participation in the trial but cannot be causally related to the intervention (since, although they may be diagnosed after the infant joins the trial, they will have occurred before the intervention takes place), and therefore for the purposes of this trial they will not be considered SAEs.

11.3. Foreseeable serious adverse events

The following are known, but rare, complications of frenotomy. If they occur, they are to be reported as SAEs:

- excessive bleeding from the incision site (a small amount of bleeding is expected)
- significant soft tissue injury such as submandibular orifice injury
- severe infection

There are also SAEs which may be expected in the trial population or as a result of their routine care. The following events therefore are foreseeable SAEs and will not be subject to SAE reporting procedures:

- · admission or extension of hospital stay due to:
 - o breastfeeding difficulties
 - o poor milk supply in the mother
 - o weight less or poor weight gain in the baby
 - o laundice

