9.6. Subsequent visits/data collection

9.6.1. Intervention

The following will be undertaken and data collected from the clinician performing the procedure on the day of the intervention:

- Intervention undertaken according to randomisation schedule and technique used (see section 9.4)
- · Bleeding following frenotomy or frenulum tear
- Post-procedure adverse events (tongue cut, salivary duct damage): measured by specific questions

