9.6.2. Routine follow-up visit

The following data will be collected from the mother at the routine follow-up visit (approximately one week post-intervention according to hospital practice):

- Mother's pain while feeding during the previous 24 hours: measured using visual analogue scale
 of the Short Form McGill Pain Questionnaire (SF-MPQ), modified into a Likert-type scale (scores
 ranging from 0 to 10) (Dennis, Jackson et al. 2014)
- Exclusive breastmilk feeding in the previous 24 hours
- Exclusive breastfeeding directly from the breast with no bottle feeds of expressed milk in the previous 24 hours
- Request for frenotomy/repeat frenotomy (defined as any further procedure on tongue-tie)
- Bleeding following frenotomy or frenulum tear
- Post-procedure adverse events (tongue cut, salivary duct damage): measured by specific questions
- Maternal anxiety or depression as indicated by the anxiety and depression dimension of EQ-5D-5L
- Maternal health-related quality of life: as elicited by the EQ-5D-5L

9.6.3. 3 month follow-up

The following data will be collected using maternal self-report (by smart-phone, tablet, computer, postal questionnaire or telephone) when the infant is 3 months of age:

- Mother's breastfeeding self-efficacy: measured using the Breastfeeding Self-Efficacy Scale Short Form (Dennis 2003)
- Mother's pain while feeding during the previous 24 hours: measured using visual analogue scale
 of the Short Form McGill Pain Questionnaire (SF-MPQ), modified into a Likert-type scale (scores
 ranging from 0 to 10) (Dennis, Jackson et al. 2014)

 Total number of contacts with any breastfeeding supporter since first referral and specific means of support used

- Infant weight
- Exclusive breastmilk feeding in the previous 24 hours
- Exclusive breastfeeding directly from the breast with no bottle feeds of expressed milk in the previous 24 hours
- Age when child last received breastmilk, to determine when and whether switch to exclusive formula feeding has occurred (McAndrew, Thompson et al. 2010)
- Time spent breastfeeding in previous 24 hours: time in minutes/hours
- Request for frenotomy/repeat frenotomy
- Bleeding following frenotomy or frenulum tear
- Post-procedure adverse events (tongue cut, scarring, salivary duct damage): measured by specific questions
- Maternal anxiety or depression as indicated by the anxiety and depression dimension of EQ-5D-5L
 Maternal health-related quality of life: as elicited by the EQ-5D-5L

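### Severe infection is a named complication of frenotomy, yet infection has no specific question at any contact and is not an outcome, so its count may be incomplete

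*Protocol*

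**What the plan says.** Section 11.3 introduces three complications with the words "The following are known, but rare, complications of frenotomy. If they occur, they are to be reported as SAEs". They are excessive bleeding, significant soft tissue injury, and "severe infection".

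The systematic collection is narrower:

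- Section 6 defines the outcome as "Post-procedure adverse events (tongue cut*, scarring, salivary duct damage*): measured by specific questions", with bleeding as a separate outcome.
- Section 9.6.1 (procedure day) collects bleeding and "Post-procedure adverse events (tongue cut, salivary duct damage): measured by specific questions".
- Section 9.6.2 (routine visit) repeats bleeding and the same two injuries.
- Section 9.6.3 (3 months) collects bleeding and "Post-procedure adverse events (tongue cut, scarring, salivary duct damage): measured by specific questions".
- Section 9.6.4 (6 months) has one item: "Any breastmilk feeding at 6 months according to maternal self-report".

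On reporting, section 11.1 says that bleeding (unless excessive), frenulum tear and "post-procedure adverse events (tongue cut, scarring, salivary duct damage) are expected in this population". It takes these out of adverse event reporting because follow-up collects them anyway. Infection is not among the exempted events. Section 11.5 sets out a procedure for SAEs only. It is triggered when staff learn of an event and closes at the first routine visit, about one week after the intervention. Appendix A marks serious/adverse event assessments at the intervention and follow-up visits, and none at 3 or 6 months.

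**The concern.** The protocol names three complications and builds a systematic question for two. The one without a question is also the one least likely to be visible on the procedure day: a cut or a bleed shows at once, whereas an infection takes time to appear.

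What is at stake is how a low infection count can be read. Section 5 describes the earlier randomised trials as totalling 302 infants, and describes existing guidance as permitting the procedure on the ground that safety concerns are lacking. A trial of 870 infants would add substantially to that safety evidence. If bleeding and injury come from questions put to every mother, while infection comes from a less specific route that closes after about a week, a low infection figure cannot be separated from low ascertainment. An analysis plan cannot recover data that were never collected.

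**Working it through.** **Step 1. The section 11.3 complications against the collection lists.**

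| Complication in 11.3 | 9.6.1 procedure day | 9.6.2 routine visit | 9.6.3 3 months | 9.6.4 6 months | Outcome in section 6 |
|---|---|---|---|---|---|
| Excessive bleeding | bleeding item | bleeding item | bleeding item | none | yes |
| Significant soft tissue injury | tongue cut, duct damage | tongue cut, duct damage | the same plus scarring | none | yes |
| Severe infection | none | none | none | none | no |

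**Step 2. The routes that remain for infection.**

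| Infection | Up to first routine visit | After it, to 3 months |
|---|---|---|
| Severe, or serious under 11.2 | Mandatory SAE (11.3, 11.5), with assessments scheduled in Appendix A: countable by arm | Outside the SAE window; could appear as an admission in the resource-use item, no reason stated |
| Non-serious | Fits the 11.1 definition of an adverse event and is not exempted; Appendix A schedules an assessment, but no recording procedure is described | Could appear as a GP visit in the resource-use item, no reason stated |

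The top left cell is covered. The lower left cell is partly covered. The right-hand column is not covered in any form that identifies infection.

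**Step 3. Arm size.** The plan gives no infection rate, so its only figure to reproduce is the sample size (section 12.1: 70% v 80%, 90% power, 5% level; two-sided by section 12.3).

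- n per group = [1.960·√(2·0.75·0.25) + 1.2816·√(0.70·0.30 + 0.80·0.20)]² / 0.10² = (1.2002 + 0.7795)² / 0.01 ≈ 391.9, so 392 per group and 784 in total, as stated.
- 784/0.95/0.95 = 868.7 and 784/0.90 = 871.1, both consistent with the stated 870.
- With 1:1 allocation (section 9.4), 870/2 = 435 infants per arm.

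**Step 4. What full ascertainment would allow (illustration).** With zero infections among 435:

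- one-sided 95% upper limit: 1 − 0.05^(1/435) = 0.69% (rule of three: 3/435 = 0.69%);
- two-sided 95% upper limit: 1 − 0.025^(1/435) = 0.84%.

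**Step 5. Whether the under-count can be sized.** Both the true rate and the share captured have to be assumed. Expected cases in the frenotomy arm are 435 × rate, and counted cases are that number × capture.

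| Assumed rate | Expected | Counted at 50% capture | Counted at 25% capture |
|---|---|---|---|
| 0.1% | 0.4 | 0.2 | 0.1 |
| 0.5% | 2.2 | 1.1 | 0.5 |
| 1% | 4.4 | 2.2 | 1.1 |
| 2% | 8.7 | 4.4 | 2.2 |

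The shortfall runs from zero (full capture) to 8.7 cases (2% rate, no capture). Nothing in the protocol narrows that range.

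**The case against.** The strongest reply is that the specific questions cover events that section 11.1 has removed from adverse event reporting. Infection was not removed, so it stays in the general route: it meets the adverse event definition, and Appendix A schedules assessments at two visits. Severe infection is a mandatory SAE, any inpatient admission within the window is serious under section 11.2, and section 11 gives the DMC review of SAE reports. The case report forms are not shown and might include an infection prompt. The protocol names only severe infection as a known complication, so asking about milder grades is a choice rather than the repair of a contradiction.

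Much of this stands, and it rules out three stronger readings that a reader might infer:

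- That the trial cannot report any infection rate. It can report severe infection by arm to about one week.
- That nobody is asked. Scheduled safety assessments exist, and the wording of their forms cannot be checked.
- That some 4 to 9 cases would go uncounted (435 × 1% = 4.4; 435 × 2% = 8.7). This needs an assumed rate of 1% to 2% and no capture at all. The protocol gives no such rate, and it provides routes that should capture some cases.

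What the reply does not answer is the gap after the first routine visit, and the missing procedure for recording a non-serious infection before it. Section 7 allows extraction from hospital records, but infection is not a listed outcome to extract.

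**Conclusion.** The point holds in a limited form. Infection is the only one of the three complications in section 11.3 with no specific question at any contact and no place among the outcomes. Severe infection up to about one week is reportable and countable by arm. Non-serious infection has no described recording procedure, and later infection of any grade is not solicited and would be unidentifiable in the resource-use data as described. The infection count may therefore be incomplete, by an amount that cannot be derived from the protocol.

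The limits of 0.69% and 0.84% show only what full ascertainment with zero events would support. They assume that all 435 infants allocated to frenotomy are assessed. The conclusion also assumes that the unseen forms follow the lists in section 9.6. This is a cheap improvement to safety ascertainment. It does not affect the primary analysis.

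**What to change.** 1. Add one specific question on mouth or procedure-site infection (none / treated / admitted) to the lists in 9.6.2 and 9.6.3, worded identically for both arms. Mothers are intended to be masked, so the comparison between arms is fair.
2. Add infection to the post-procedure adverse events outcome in section 6.
3. Report it by arm, including to the DMC. Naming the DMC is useful because section 11.5 forwards individual reports to it only for SAEs that are both related and unforeseeable, and section 11.4 treats the events listed in 11.3 as foreseeable.

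The cost is one question on two existing contacts and one line in the outcome table. The downside is that some unrelated oral infections, such as thrush, will be reported in both arms. Showing the results by arm deals with that.
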